2.8.4.4 Columbia Suicide Severity Reporting Scale (C-SSRS)

C-SSRS data will be mapped to Columbia Classification Algorithm for Suicide Assessment (C-CASA) as per FDA guidance on suicidality (Food and Drug Administration 2010). The proportion of patients who have committed suicide, attempted suicide, done preparatory actions toward imminent suicidal behavior, suicidal ideation, and self-injurious behavior without suicidal intent will be summarized by treatment arm. The number of patients with SAEs referring to a positive suicidal evaluation will be summarized by treatment arm.

2.9 Pharmacokinetic endpoints

The PAS will be used in all pharmacokinetic data analysis and summary statistics.

As sparse pharmacokinetic sampling is performed in this study, traditional non-compartmental analysis will not be performed to calculate pharmacokinetic parameters. Plasma concentration data of osilodrostat will be listed by subject, visit, incident dose and nominal sampling times. Descriptive statistics of plasma concentrations will be provided by incident dose, visit and nominal sampling times, and will include arithmetic and geometric mean, median, SD, CV%, geometric CV%, minimum and maximum. Zero concentrations will not be included in the geometric mean calculation.

Listing of all PK parameters will be provided by patient and visit:

- Ctrough as defined by pre-dose concentration collected within 0.5h prior to dosing and within 9h to 15h after the previous dose and
- and Cmax, defined as concentration collection within 1-2hr post-dose.

Plasma concentrations of osilodrostat will be expressed in ng/mL. Missing concentration values will be labeled as such in data listings. Concentrations below the limit of quantitation (LLOQ) will be treated as zero in summary statistics and reported as zero in data listings.

[REDACTED]

[figure not shown]
[REDACTED]

2.11 Patient-reported outcomes

The CushingQoL score is identified as the primary PRO variable of interest. EQ-5D utility index and visual analogue scale (VAS) scores, and Beck Depression Inventory-II (BDI) total score are identified as secondary PRO variables of interest. The FAS will be used for analyzing PRO data. No multiplicity adjustment will be applied.

Descriptive statistics will be used to summarize the actual and change from baseline for the scores at each scheduled assessment including critical time points such as from baseline to Week 12 and Week 48, from Week 12 to Week 36 and from Week 36 to Week 48 etc.

[REDACTED]

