10.5.7 Patient-reported outcomes

The CushingQoL score is identified as the primary PRO variable of interest. EQ-5D utility index and visual analogue scale (VAS) scores, and Beck Depression Inventory-II (BDI) total

[figure not shown]
score are identified as secondary PRO variables of interest. The FAS will be used for analyzing PRO data. No multiplicity adjustment will be applied.

Change from baseline in the CushingQoL score during Study Period 1 and 2 will be analyzed using a linear mixed effect model for longitudinal data to assess the treatment effect over time. The differences in least square means between osilodrostat and placebo arm, and the corresponding 2-sided 95% confidence interval (CI) at each time point will be presented. Descriptive statistics will be used to summarize the raw and absolute change from baseline for the scores at each scheduled assessment including critical time points such as from baseline to Week 12 and Week 48, from Week 12 to Week 36 and from Week 36 to Week 48 etc. during both Core phase (Study Period 1 and 2) and the optional extension phase.

Similar analyses will be performed for EQ-5D utility index and visual analogue scale (VAS) scores, and Beck Depression Inventory-II (BDI) total score.

Missing items data in a scale will be handled based on each instrument manual. Additional details for handling missing items data will be specified in the analysis plan for instruments with no missing data handling criteria in the instrument manual.

No imputation will be applied if the total scores are missing at a visit. Patients with baseline and at least one non-missing post-baseline assessments during the Core phase will be included in the linear mixed effect model analysis. All available data until completion or early discontinuation during Core phase will be used in the linear mixed effect models analyses with missing scores at any time point are assumed to be missing-at-random (MAR).

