Clinical Development

LCI699/Osilodrostat

CLCI699C2302 / NCT02697734

A Phase III, multi-center, randomized, double-blind, 48 week study with an initial 12 week placebo-controlled period to evaluate the safety and efficacy of osilodrostat in patients with Cushing's disease

Statistical Analysis Plan (SAP)

Author: Trial statistician, [REDACTED]
Document type: SAP Documentation
Document status: Final v1.0 - Amendment 1
Release date: 01-Apr-2019
Number of pages: 35

Property of Novartis
For business use only
May not be used, divulged, published or otherwise disclosed
without the consent of Novartis

Document History – Changes compared to previous final version of SAP

Date	Time point	Reason for update	Outcome for update	Section and title impacted (Current)
22-Jun-2016	Prior to FPFV	Creation of final version	Creation of first version	All
01-Apr-2019	Prior to DBL & unblinding	Creation of amendment 1	Change from baseline analysis of serum, salivary and hair cortisol added as a trial objective.	1.2 Study objectives and endpoints 2.7.8 Assess the change from baseline in serum, salivary and hair cortisol levels
			Updated description of the extension period to allow for patients remaining beyond week 96	1.1.4 Extension phase
			Removal of longitudinal model of change in mUFC for the core and extension period.	2.7.2 Assess the change in mUFC during the Core and Extension periods of the study
			Removal of visit window requirement	2.1.1 General definitions
			Removal of section 2.4.1.3	2.4.1.3 Dose level of osilodrostat
			Removal of sections 2.10.1 and 2.10.2, and update of 2.10.3	
			Update of PK collection windows	2.2.4 Pharmacokinetic analysis set 2.9 Pharmacokinetic endpoints
			Removal of PRO longitudinal models	2.11 Patient reported outcomes
			Language and grammar updates	Multiple sections

Table of contents

Table of contents	3
List of abbreviations	6
1 Introduction	8
1.1 Study design.....	8
1.1.1 Screening period.....	9
1.1.2 Period 1 (Weeks 1-12): double-blind, placebo-controlled period.....	9
1.1.3 Period 2 (Weeks 13-48): single arm, open-label treatment period	9
1.1.4 Extension phase:.....	10
1.2 Study objectives and endpoints	10
2 Statistical methods.....	12
2.1 Data analysis general information	12
2.1.1 General definitions	13
2.2 Analysis sets	15
2.2.1 Full Analysis Set	15
2.2.2 Safety Set	15
2.2.3 Per-Protocol Set	15
2.2.4 Pharmacokinetic analysis set.....	16
2.2.5 Withdrawal of informed consent	17

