In the SAP, clarification is made that efficacy will be summarized by randomized treatment arms during the placebo-control period. The same analysis will be performed by randomized treatment arms and for overall patients during the open-label period.

Safety will be summarized by randomized treatment arms during the placebo-control period. For the overall study period, only safety data associated with osilodrostat treatment will be summarized, which means safety data in placebo-arm collected during placebo-control period will be excluded from the analysis.

5 Appendix

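### The core SAP drops the protocol's mixed model for patient-reported outcomes without declaring it in Section 4, leaving no planned between-arm quality-of-life estimate for the blinded period

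*SAP*

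**What the plan says.** Protocol 10.5.7 ranks the instruments: "The CushingQoL score is identified as the primary PRO variable of interest", with EQ-5D (index and VAS) and BDI-II as secondary PRO variables. It then names the analysis: "Change from baseline in the CushingQoL score during Study Period 1 and 2 will be analyzed using a linear mixed effect model". The output is to be "The differences in least square means between osilodrostat and placebo arm, and the corresponding 2-sided 95% confidence interval (CI) at each time point". For the remaining scores: "Similar analyses will be performed for EQ-5D utility index and visual analogue scale (VAS) scores, and Beck Depression Inventory-II (BDI) total score". The model takes missing scores as missing at random.

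The core SAP (Amendment 1, 1 April 2019) keeps the ranking of the instruments but not the model. Section 2.11 offers only this: "Descriptive statistics will be used to summarize the actual and change from baseline for the scores at each scheduled assessment". The entry in its document history reads "Removal of PRO longitudinal models", dated before database lock and unblinding, with no reason given. Section 4 of the same SAP, the place for changes to the protocol's analyses, says that "clarification is made that efficacy will be summarized by randomized treatment arms during the placebo-control period", adds how safety is grouped by arm and period, and is silent on the PRO models.

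The final SAP (1 December 2020), which states that it is based on the December 2019 protocol, is also descriptive only in Section 2.9, and its Section 4 does not mention the PROs either.

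**The concern.** Two governing documents prescribe different analyses for a named secondary objective, and nothing explains the difference. Period 1 is the only blinded, randomised comparison in the trial, and the schedule is built to use it: CushingQoL and BDI-II are taken at Day 1 and Weeks 2, 5, 8 and 12, and protocol 7.2.6 shortens the CushingQoL recall period to one week so that it picks up change sooner. After Week 12 both arms receive osilodrostat, so a drug-versus-placebo contrast on quality of life can come only from these visits.

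The likely consequence is that two arm means appear side by side in the report and readers form their own difference, with no planned interval and no adjustment for baseline. In a trial of this size that invites over-reading in either direction.

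**Working it through.** The documents give no power, SD or target difference for any PRO, so there is no plan figure to reproduce. The check is a comparison of text, followed by two illustrative calculations.

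**1. The plans side by side**

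| Element | Protocol 10.5.7 | Core SAP 2.11 |
|---|---|---|
| Primary PRO | CushingQoL | CushingQoL |
| Method | Linear mixed model, Periods 1 and 2 | Descriptive statistics |
| Between-arm difference | LS-mean difference at each time point | None planned |
| 95% CI for the difference | Yes | None planned |
| BDI-II, EQ-5D | Similar analyses | Descriptive statistics |
| Missing total scores | Missing at random, within the model | No model |

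**2. Order of events**

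- 1 April 2019: core SAP Amendment 1 removes the models.
- 20 December 2019: Protocol Amendment 2. Its change list touches the opening of Section 10, 10.5.2.2 and 10.5.3.4, but not 10.5.7, so the model stays in the protocol.
- 1 December 2020: the final SAP is written against that protocol and is descriptive only.

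**3. Is descriptive-only the rule for secondary endpoints?** No. Core SAP 2.7.5 keeps, for the cardiovascular and metabolic parameters, a mean difference between the randomised arms over the placebo-controlled period, adjusted for baseline and with a 95% CI.

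**4. What data exist?** Protocol Tables 7-1a and 7-11 schedule CushingQoL and BDI-II at Day 1 and Weeks 2, 5, 8 and 12, and EQ-5D at Day 1 and Week 12. Patients who stop drug in Period 1 keep the matching follow-up visits.

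**5. Precision of a Week 12 difference.** Planned arms are 46 and 23 (core SAP 1.1). For an unadjusted difference in change scores:

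half-width = 1.96 × SD × √(1/23 + 1/46) = 1.96 × 0.2554 × SD ≈ 0.50 SD.

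With 42 and 21 patients it is 1.96 × √(1/21 + 1/42) ≈ 0.52 SD. The SD of change is not in the documents. For assumed values of 10, 15 and 20 points on the 0–100 CushingQoL scale, 46 versus 23 gives about ±5.0, ±7.5 and ±10.0 points.

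**6. Effect of baseline adjustment (illustration only).** If baseline and follow-up variances are equal and their correlation is r, the variance of a baseline-adjusted difference relative to a change-score difference is

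(1 − r²) / [2(1 − r)] = (1 + r)/2.

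For assumed r of 0.4, 0.5, 0.6 and 0.7 this is 0.70, 0.75, 0.80 and 0.85. The half-width in step 5 would then fall from 0.50 SD to between 0.50 × √0.70 ≈ 0.42 and 0.50 × √0.85 ≈ 0.46 SD of change. Neither r nor the equal-variance condition can be checked from the documents.

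**The case against.** The best defence is that the PRO objective asks for change to be assessed by arm and overall, whereas the objective on time to first control asks for a comparison. Summaries by arm meet the PRO objective and endpoint as worded. The PROs carry no multiplicity control, and the sample size rests on cortisol response alone. Protocol Amendment 2 was mainly about the end of the study, so the model text in 10.5.7 may be carry-over rather than a renewed commitment. Part of the protocol model also suits the trial poorly: in Period 2 an arm difference is no longer drug against placebo.

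Much of this stands, and it limits the point to a secondary matter. It does not remove it. The cardiovascular and metabolic objective is also worded as an assessment, yet the SAP keeps a between-arm estimate there. The weakness of the Period 2 contrast is a reason to narrow the model to Period 1, not to drop the Period 1 contrast. Carry-over text in a current protocol still needs aligning.

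Readers might infer several stronger things that the documents do not support:

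- **That the change was hidden or driven by results.** It is in the SAP's document history, dated before database lock and unblinding.
- **That the trial cannot say anything about quality of life against placebo.** Results are given by arm, and core SAP 2.1 includes mean and SD, so an unadjusted difference can be derived.
- **That missing visits are handled by complete cases.** Section 2.11 summarises each scheduled assessment and requires no full set of visits. Core SAP Table 1-1 refers to the last measurement before early discontinuation.
- **That the trial loses a known amount of precision.** The ratios in step 6 of the working rest on assumed correlations and concern a raw-change contrast that the SAP does not plan.

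Text is blacked out after Section 2.11 and cannot be read. The log entry makes it unlikely that the model survives there.

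**Conclusion.** The point holds as an undeclared and unexplained mismatch between protocol and SAP on a secondary endpoint. Its practical effect is that no between-arm estimate, confidence interval or baseline adjustment is planned for quality of life in the blinded period, although the protocol specifies an estimate and the data are collected. Had the contrast been kept, its unadjusted 95% interval would be about ±0.50 SD of change at the planned enrolment. That follows from the arm sizes and a normal approximation; any figure in points rests on an assumed SD. Primary and key secondary conclusions do not depend on it. The change should be made, but it is not critical to the trial's main claims.

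**What to change.** In core SAP 2.11, reinstate a Period 1 between-arm analysis based on the protocol model:

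- CushingQoL and BDI-II: change from baseline at Weeks 2, 5, 8 and 12, with baseline score, irradiation stratum, arm, visit and arm-by-visit. Report the Week 12 difference with its 95% CI.
- EQ-5D index and VAS: a baseline-adjusted Week 12 difference with 95% CI, because Week 12 is the only scheduled on-treatment assessment in Period 1.
- Label all of these as outside multiplicity control.
- Keep Period 2 descriptive.

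This is narrower than the protocol model, which spans both periods, and it names covariates that 10.5.7 does not. List that narrowing, with its reason, in SAP Section 4, and align protocol 10.5.7. The final SAP records that the core results have already been reported, so if the change is made now, say which elements come from the protocol and which were chosen after unblinding.

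The cost is a paragraph of SAP text, one model per score and an edit to the protocol section. No new data are needed.

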2.14 Interim analysis

The study will have no planned interim analysis for efficacy. The DMC will conduct periodic safety data reviews and dosing review as outlined in DMC charter.

3 Sample size calculation

Eligible patients will be stratified at randomization according to history of pituitary irradiation (yes/no). Based on the LCI699C2201 study, it is assumed that approximately 20% of randomized patients will have a history of pituitary radiation.

With 2:1 randomization ratio, to detect a difference of 45% in complete response rate between 60% in osilodrostat arm and 15% in placebo arm (equivalent odds ratio equals 8.5), a sample size of 42 patients in osilodrostat arm and 21 patients in placebo arm will provide 91% power based on a 1-sided CMH exact test at the 0.025 level. In order to adjust for drop-outs, an additional 10% patients will be enrolled. Thus a total of approximately 69 patients will be enrolled in the study.

The analysis of the key secondary objective will be based on the 2-sided 95% confidence interval constructed using the Clopper-Pearson exact method. If the lower bound of this 95% confidence interval is $\geq 30\%$, the null hypothesis will be rejected and the complete response rate will be considered at least 30% at Week 36. Both the SOM230G2304 trial of Pasireotide LAR and the SOM230B2305 trial of Pasireotide s.c. were powered to show a response rate where the lower bound of the 95% confidence interval was $\geq 15\%$. Therefore an increase in this lower bound of the 95% confidence interval to a threshold of $\geq 30\%$ would provide a significant improvement in clinical benefit to this patient arm.

The above testing on the key secondary objective will only be carried out if the null hypothesis for the primary objective is rejected. This sequential procedure will ensure preservation of the overall 2-sided type 1 error at 5%.

Assuming a 60% complete response rate at Week 36, and less than 50% discontinuation rate of patients in placebo arm prior to Week 12. For the 69 patients in the pooled population, there is higher than 98% chance that the lower bound of 2-side 95% exact CI (based on Clopper-Pearson method) of the observed response rate is larger than 30%.

4 Change to protocol specified analyses

In the SAP, clarification is made that efficacy will be summarized by randomized treatment arms during the placebo-control period. The same analysis will be performed by randomized treatment arms and for overall patients during the open-label period.

Safety will be summarized by randomized treatment arms during the placebo-control period. For the overall study period, only safety data associated with osilodrostat treatment will be summarized, which means safety data in placebo-arm collected during placebo-control period will be excluded from the analysis.

5 Appendix

5.1 Imputation rules

Partial dates will remain partial in the data listings. For the purpose of analysis, the following imputation rules will be used to impute the partial dates.

5.1.1 Study drug

Any partial dates or gaps between dates should be resolved for analysis purpose. The end date of study drug is derived by using the last non-zero dose end date from the dose administration record CRF page. If after DBL the partial dates still exist for end date, the imputation rule is as below:

If month and year is present, but day is missing, set the end date to be the first day of the month. If after imputation of day, study medication end date is earlier than study medication start date set study medication end date to study medication start date.

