2.1.1 General definitions

Study drug

Through out the SAP, investigational drug refers to osilodrostat, and study treatment/ study drug refers to osilodrostat or placebo.

Date of study treatment

The start date of study treatment is defined as the first date when a nonzero dose of study treatment was administered and recorded on DAR eCRF. The date of first administration of study treatment in period 1 will be referred as the start date of study treatment.

The last date of study treatment is defined as the last date when a nonzero dose of study drug was administered and recorded on DAR eCRF.

Study day

Study day is used to represent an evaluation, a measurement or an event (e.g. AE onset, laboratory abnormality occurrence, disease progression, etc). The study day is calculated as

Study day = date of assessment –start date of study treatment + 1 (if date of assessment is after start date of study treatment)

Study day = date of assessment –start date of study treatment (if date of assessment is before start date of study treatment)

For any assessment or events such as baseline characteristics or medical history that is supposed to occur prior to start date of the study treatment, study day will be negative. There is no Day 0 defined.

Study day associated with a UFC assessment

The study day associated with a UFC assessment at any particular visit is defined as the study day of the last UFC sample collection for that visit.

Time unit

A year length is defined as 365.25 days. A month length is 30.4375 days (365.25/12). If duration is reported in months, duration in days will be divided by 30.4375. If duration is reported in years, duration in days will be divided by 365.25.

Baseline

Baseline values for efficacy and safety evaluations are defined as the last assessment available before or on the start date of study treatment. If patients have no assessments as defined above, the baseline result will be missing.

Follow up

Regular safety follow-up is scheduled at 30 days after the last date of study treatment. In addition, for patients who discontinued study treatment during Period 1 (Weeks 1 to 12), reasonable efforts should be made to follow the patients and perform the assessments as indicated in protocol visit evaluation schedule table (protocol Table 7-1a) up to and including Week 12. The data collected during the follow up visits in Period 1 will be used as sensitivity analysis for efficacy, and will be used for safety.

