2.8 Safety analyses

The assessment of safety will be based mainly on the frequency and severity of AEs and on the number of laboratory values that fall outside of pre-determined ranges. Other safety data (e.g. ECG, vital signs, and special tests) will also be presented. All safety outputs will use the SS, which consists of all patients who received at least one dose of osilodrostat or placebo. Safety data will be presented by two different periods in different treatment groups as described below.

- Placebo-control period: osilodrostat arm, placebo arm

- Overall study period: osilodrostat arm, placebo arm excluding placebo-control period, and overall patients (excluding safety data of placebo arm collected during placebo-control period)
 - * Safety summarized during overall study period focuses on safety of osilodrostat treatment, safety of placebo arm is summarized during placebo-control period.

The overall observation period will be divided into three mutually exclusive segments:

- pre-treatment period: from day of patient's informed consent to the day before first dose of study medication
- on-treatment period: from day of first dose of study medication to 30 days after last dose of study medication
- post-treatment period: starting at 31 days after last dose of study medication.

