2.8.1 Adverse events (AEs)

Summary tables for adverse events (AEs) have to include only AEs that started or worsened during the on-treatment period, the *treatment-emergent* AEs. However, all safety data (including those from the pre and post-treatment periods) will be listed and those collected during the pre-treatment and post-treatment period are to be flagged.

The incidence of treatment-emergent adverse events (new or worsening from baseline) will be summarized by system organ class and or preferred term, severity (based on CTCAE version 4.03 grades), type of adverse event, relation to study treatment.

Serious adverse events, non-serious adverse events and adverse events of special interest (AESI) during the on-treatment period will be tabulated.

All AEs, deaths and serious adverse events (including those from the pre and post-treatment periods) will be listed and those collected during the pre-treatment and post-treatment period will be flagged.

AEs will be summarized by number and percentage of subjects having at least one AE, having at least one AE in each primary system organ class (SOC) and for each preferred term (PT) using MedDRA coding. A subject with multiple occurrences of an AE will be counted only once in the respective AE category. A subject with multiple CTCAE grades for the same preferred term will be summarized under the maximum CTCAE grade recorded for the event.

In AE summaries the primary system organ class will be presented alphabetically and the preferred terms will be sorted within primary SOC in descending frequency. The sort order for the preferred term will be based on their frequency in the osilodrostat arm.

The following adverse event summaries will be produced by treatment; overview of adverse events and deaths (number and % of subjects who died, with any AE, any SAE, any drug reductions/interruptions), AEs by SOC and PT, summarized by relationship (all AEs and AEs related to study treatment), seriousness (SAEs and non-SAEs), leading to treatment discontinuation, leading to dose interruption/adjustment, requiring additional therapy and leading to fatal outcome. In addition, for the summary of serious and non-serious adverse events the number of occurrences will be produced (an occurrence is defined as >1 day between start and prior end date of record of same preferred term).

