5.1.2 AE date imputation

Summary tables for adverse events (AEs) have to include only AEs that started or worsened during the on-treatment period, the treatment-emergent AEs. However, all safety data (including those from the post-treatment period) will be listed and those collected during the pre-treatment and after 30 days of post-treatment period or safety follow-up whichever is later are to be flagged.

Any missing onset date, causality, or severity must be queried for resolution. Unsolved missing values will be imputed according to the following:

AE end date imputation:

1. If the AE end date month is missing, the imputed end date should be set to the earliest of the (treatment follow up period date, 31DECYYYY, date of death).
2. If the AE end date day is missing, the imputed end date should be set to the earliest of the (treatment follow up period date, last day of the month, date of death).
3. If AE year is missing or AE is ongoing, the end date will not be imputed.

AE start date imputation:

1. If the AE start date year value is missing, the date uncertainty is too high to impute a rational date. Therefore, if the AE year value is missing, the imputed AE start date is set to NULL.
2. If the AE start date year value is less than the treatment start date year value, the AE started before treatment. Therefore:

- a. If AE month is missing, the imputed AE start date is set to the mid-year point (01JulYYYY).
 - b. Else if AE month is not missing, the imputed AE start date is set to the mid-month point (15MONYYYY).
3. If the AE start date year value is greater than the treatment start date year value, the AE started after treatment. Therefore:
- a. If the AE month is missing, the imputed AE start date is set to the year start point (01JanYYYY).
 - b. Else if the AE month is not missing, the imputed AE start date is set to the later of (month start point (01MONYYYY), AE start reference date + 1 day).
4. If the AE start date year value is equal to the treatment start date year value:
- a. And the AE month is missing the imputed AE start date is set to the AE reference start date + 1 day.
 - b. Else if the AE month is less than the treatment start month, the imputed AE start date is set to the mid-month point (15MONYYYY).
 - c. Else if the AE month is equal to the treatment start date month or greater than the treatment start date month, the imputed AE start date is set to the later of (month start point (01MONYYYY), AE start reference date + 1 day).

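### Partial-date rules in both SAPs can drop some AEs that start after the last dose, and some placebo-arm AEs of uncertain onset, from the osilodrostat AE tables

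*SAP*

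**What the plan says.** The core SAP (01-Apr-2019) and the final SAP (01-Dec-2020) carry the same rules.

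- **Last dose (5.1.1).** Partial dates should first be resolved, and the rule is a fallback for what remains: "If after DBL the partial dates still exist for end date, the imputation rule is as below". For such a leftover date the instruction is: "If month and year is present, but day is missing, set the end date to be the first day of the month". An imputed date that precedes the first dose is reset to the first dose.
- **AE window (2.8, 2.8.1).** The segments are "on-treatment period: from day of first dose of study medication to 30 days after last dose of study medication" and, after it, "post-treatment period: starting at 31 days after last dose of study medication". Section 2.8.1 ties the tables to the first of these: "Summary tables for adverse events (AEs) have to include only AEs that started or worsened during the on-treatment period". Other AEs are listed and flagged.
- **AE start date (5.1.2, rule 4).** The condition is "If the AE start date year value is equal to the treatment start date year value", and the instruction under 4a is: "And the AE month is missing the imputed AE start date is set to the AE reference start date + 1 day". Section 2.1.1 gives one treatment start: "The date of first administration of study treatment in period 1 will be referred as the start date of study treatment". In the placebo arm that is a placebo dose. The AE reference start date is not defined. The only reference start date with a definition (5.1.3.2) is the day after the last dose, and it concerns post-treatment events other than AEs and concomitant medication.
- **Overall-period safety.** Core SAP 2.8 and 4, and final SAP 2.8, leave out placebo-arm data from the placebo-controlled period. The final CSR does not repeat the placebo-period safety tables.
- **A second limit (5.1.2).** The text on flagging AEs uses the later of 30 days and the safety follow-up, whereas 2.8 uses 30 days alone.

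**The concern.** The last-dose rule picks the earliest day compatible with the record. The AE window hangs on that date, so an error can only shorten it. The SAPs give no reason for the choice, and their other partial end dates lean late. An AE end date goes to the last day of the month, capped at the follow-up date or death. A concomitant-medication end date goes to the last day of the month, capped at treatment end.

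Rule 4a raises a different problem. A placebo-arm patient has two relevant starts, placebo on Day 1 and osilodrostat from Week 12, but the plan defines only the first. An AE of unknown month is placed next to that first start, inside the period that the osilodrostat summary excludes.

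In both cases the affected osilodrostat AE counts can only fall, which is the non-conservative direction for a safety table. The trial is small: one patient is 1/69 = 1.4% of the planned total and 1/23 = 4.3% of the planned placebo arm.

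**Working it through.** The plan gives no figure to reproduce, so this is calendar arithmetic on the stated rules. Equally likely calendar dates in a 365-day year are an assumption.

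**Last-dose rule.** Let d be the true day of the month of the last dose.

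- True window end = last dose + 30 days. Imputed window end = first of that month + 30 days. Days lost = d − 1, so 0 to 30.
- A month of n days contributes n(n − 1)/2 lost days. Over the year: 7 × 465 + 4 × 435 + 1 × 378 = 3255 + 1740 + 378 = 5373. The mean is 5373/365 = 14.7 days, and 14.7/30 = 49% of the 30-day tail.
- Example: with a true last dose on 31 January 2018 the window runs to 2 March. With the imputed date it ends on 31 January.
- Exposure (core and final SAP 2.4.1.1) ends at the last treatment date, so it falls by the same days: on average 14.7/7 = 2.1 weeks per affected patient.
- If first and last dose fall in the same month, the reset to the first dose makes the loss smaller.

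*Which events can be lost.* First of month + 30 days is the 31st or later, so the imputed window always covers the rest of the stopping month. For 0 of 365 possible last-dose dates does a dosing day fall outside it. Only an AE that starts after the true last dose can drop out of the tables. Deaths are reported on and after treatment (2.8.2 in both SAPs). Laboratory summaries run to the later of 30 days and the safety follow-up (2.8.3 in both).

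**AE start rule 4a, placebo arm.** Let S be the Period 1 start, and suppose the AE reference start date means S.

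- The imputed start is S + 1 = Day 2. The switch is at S + 84 = Day 85 (Table 2-1), so Day 2 always precedes it.
- Rule 4a applies only within the calendar year of S. A true osilodrostat onset in that year needs S + 84 to fall by 31 December. That holds for 365 − 84 = 281 start dates (77%), up to 8 October. For the other 84 (23%) nothing can be misplaced.
- Example: start 1 March 2018, switch 24 May 2018. A 2018 AE of unknown month becomes 2 March, although 222 days of that year fall on or after the switch.
- If the AE year is later than the start year, rule 3a gives 1 January, which precedes the switch for 83 of 365 start dates (23%).
- If only the day is missing, rules 3b and 4c give the first of the month. In the switch month that precedes the switch unless the switch falls on the 1st: 353/365 = 97% of start dates.

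In the core CSR, a rule 4a event of this kind is counted under placebo in the placebo-controlled table. In the final CSR, given the exclusion in 2.8, it appears in no AE summary table. It stays in the listings of both.

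**The case against.** The strongest reply is that these are last-resort rules. Section 5.1.1 wants partial dates resolved, and 5.1.2 requires a query before imputation. The protocol also gives several sources for the stop date: a patient diary of each dose (6.1.1), dose records in the eCRF (6.6), and the recorded stop date and IRT registration within 2 days (7.1.4). This stands. Nothing in the documents shows how many dates stay partial, or that they cluster among patients who leave early.

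Three further replies stand in part.

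- First-of-month is the cautious choice for exposure. Last-of-month without a cap would overstate exposure by 0 to 30 days, mean 14.7. That is a reason to cap it; it does not justify cutting the AE window.
- The concomitant-medication rule concerns another variable, so the contrast is not a contradiction. It still leaves the opposite choice for study drug unexplained.
- The later limit in 5.1.2 could soften the loss of AEs. But it is written for flagging and disagrees with 2.8, which defines the tables.

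A reader might infer more than the documents support:

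- *Deaths and laboratory values are lost too.* They are not, for the reasons in the working.
- *AEs that led to stopping disappear.* An AE that began during dosing always stays inside the window.
- *Rule 4a works against osilodrostat safety in general.* In the osilodrostat arm (46 of 69 planned) Day 2 makes an ambiguous AE treatment-emergent, which is conservative.
- *The 36 of 48 Core weeks on osilodrostat measure how often a placebo-arm AE is misplaced.* They do not, because rule 4a is confined to one calendar year.

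**Conclusion.** The point holds in a limited form. For a last-dose date that stays partial, the AE window can close 0 to 30 days early (mean 14.7 under evenly spread dates) and exposure is understated by the same amount. The only AEs at risk are those that start after the true last dose. For a placebo-arm AE of unknown month in the start year, an onset on osilodrostat can be moved to Day 2 and out of the overall-period osilodrostat tables. This second part depends on reading the undefined AE reference start date as the Period 1 start. That is the natural reading, but programmers could differ.

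Removal is possible, not certain. The number of affected dates is not given and is probably small, so no effect on a reported rate can be computed. The case for acting is that the direction is non-conservative and the repair is cheap.

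**What to change.** 1. **5.1.1, both SAPs.** Impute the last day of the month, capped at the earliest of the EOT or last contact date, death and data cut-off.
2. **5.1.2, both SAPs.** Define the AE reference start date. For a placebo-arm AE whose partial start date and (imputed) end date do not rule out onset on or after the first osilodrostat dose, use for the overall-period tables the later of the earliest compatible date and the first osilodrostat dose date. This also covers the ambiguous cases under rules 3a, 3b and 4c. State how such an AE is handled in the placebo-controlled table, so that it is not unknowingly counted twice.
3. **2.8 against 5.1.2.** Reconcile the strict 30-day window with the limit that extends to the safety follow-up.

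The cost is a few lines of text and programming, with no new data. The downside is that exposure may be slightly overstated where the cap does not bind, and a few ambiguous AEs will be attributed to osilodrostat conservatively.
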